**Table 1. Data collection by objective, location, schedule and mode of collection, and compensation.**

Objective	Data collection	Location	Schedule and mode of collection	Compensation
1,2	Enrollment Questionnaire	Participating hospital	Self-administered within 48 hrs of delivery	\$80 in cash at OSUWMC; \$80 in electronic gift card at Emory-affiliated Hospital
1	Milk Let-Down Questionnaire	Participating Hospital / text, telephone, email	Interviewer administered ≤3 times daily in person at OSUWMC or Emory-affiliated hospital, then daily via text, telephone or email during the first 7 days postpartum until lactogenesis stage II occurs	One payment of \$30 in electronic gift card at all sites
1,2	Follow-up Questionnaire	Online	Self-administered at 1, 2, 4, 6, 9 and 12 months. Questionnaires at 1, 6 and 12 months include infant anthropometric measures* from well-child visit data	\$10 per interview in electronic gift card at all sites
1	Infant adiposity (PEA POD) and other infant measures*†	OSUWMC only	Measured by trained study staff at 4 months of age	\$40 in gift card, a branded gift (e.g., a cell phone popsocket or a pen with light) worth less than \$4.00, and either parking pass or transportation by cab to appointment

OSUWMC = Ohio State University Wexner Medical Center; \*Includes weight, length, head circumference; †Visit not completed by participants who delivered at an Emory-affiliated Hospital

## B. Study Population

We will enroll a convenience sample of 800 women. Women can enroll either prenatally or postpartum before their hospital discharge.

To enroll prenatally, women need to meet the following eligibility criteria:

- 1) Intend to deliver in the Labor and Delivery Unit at a participating ;
- 2) Are ≥18 years of age;
- 3) Speak English;
- 4) Intend to breastfeed, or express milk for their infant, for ≥6 months;
- 5) Do not want to become pregnant within the first 12 months after delivery;
- 6) Want to start use of DMPA immediately after delivery before discharge; **AND**

- 7) Intend to reside in Ohio for those who deliver at OSUWMC or intend to reside in Georgia for who deliver at an Emory-affiliated Hospital for the first 12 months after delivery.

Women will be excluded if they have any contraindications to DMPA (per package insert), which consist of the following:

- 8) Undiagnosed vaginal bleeding;
- 9) Known or suspected malignancy of breast;
- 10) Active thrombophlebitis, or current or past history of thromboembolic disorders, or cerebral vascular disease;
- 11) Liver dysfunction or disease; **OR**
- 12) Known hypersensitivity to Depo-Provera.

Women who enroll prenatally will need to rescreen following delivery to confirm their eligibility. Women enrolling after delivery or who are rescreening will need to meet criteria 2-12 above as well as the following eligibility criteria:

- 1) Are a postpartum patient in the Labor and Delivery Unit at OSUWMC or participating Emory-affiliated Hospital; **AND**
- 2) Have delivered a term, singleton infant of  $\geq 2500$  grams without any apparent health concerns.

### C. Outcome Measures

The primary outcome is time to lactogenesis stage II measured with participant reports. Chapman and Perez-Escamilla validated the accuracy of maternal perceptions of the timing of lactogenesis stage II, and we will adhere to their questions and methods. Immediately after enrollment, we will record whether women perceived that their milk “has come in” and, if so, we will capture this event to the estimated post-delivery hour. Participants will be re-asked (up to 3 times daily in person during their hospital stay and then daily via their choice of text, telephone, or email after discharge) during the first 7 days postpartum until the event occurs.

Secondary outcomes include 1) length of breastfeeding continuation, which has been negatively associated with both experiencing a delay in lactogenesis stage II and maternal perception of the adequacy of her milk production; 2) perceived need for supplementation (any and timing); and 3) use of supplementation (any and timing). We will use established questions on breastfeeding (any and exclusive feeding) from the National Immunization Survey, which also are used on the Health and Nutrition Examination Survey (NHANES).

**Table 2. Location for recruitment, screening and enrollment by prenatal and postpartum status and type of location**

Women	Type of location	Location
Prenatal	Prenatal care at primary obstetrical facilities that refer to a participating hospital for delivery	
 
• Hospital obstetrics-gynecology outpatient clinic
 
• Faculty practices
 
• Primary One health centers
 

	Local classes for pregnant women in the community	
 
• Lactation, birthing and prenatal yoga classes
 

Finally, secondary outcomes will include infant measures collected during the follow-up questionnaire (using maternal reports of data from well-child visits) and during the 4-month visit at OSUWMC. Participants enrolled at an Emory-affiliated hospital will not complete a 4-month visit because the site lacks the ADP system. The latter will include the following: 1) percent fat mass (%FM) and fat-free mass (FFM%) measured using the validated, non-invasive whole-body air displacement plethysmography (ADP) system; 2) length with a SECA 416 digital infantometer; 3) head circumference with metric tape; 4) body weight with SECA 727 digital scale; and 5) skinfold with Holtain calipers. We will ensure consistently high-quality measurement by regular monitoring, assessing reliabilities, and refresher training.	Postpartum	Through MyChart Hospital	
 
• Tour of study hospitals during pregnancy
 
• OSUWMC and participating Emory-affiliated hospitals
 

---	------------	--------------------------	---

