## **III. Objectives**

**Objective 1: To determine the effect of immediate postpartum initiation of DMPA on breastfeeding.** We hypothesize that administration of DMPA immediately postpartum (i.e., before hospital discharge) will not impair breastfeeding compared to administration beginning at 12 weeks post-delivery. To increase the likelihood of detecting a negative effect if one exists, we will evaluate the primary outcome, timing of lactogenesis stage II (onset of copious milk secretion, usually occurring within 96 hours postpartum), as well as a range of secondary outcomes: breastfeeding duration, perceived need for supplementation, use of supplementation, perceived adequacy of milk production, and infant anthropometric measures, including body composition with whole-body air displacement plethysmography (OSUWMC site only). Sensitivity analysis will evaluate 1) excluding women in the open control arm and 2) determining whether the findings differ by race.

**Objective 2: To determine the effect of immediate postpartum initiation of DMPA on contraception use.** We hypothesize that putative DMPA use (i.e., blinded assignment to intervention or placebo arms) will put women on a better trajectory of contraception use by intervening during a time when they likely are highly motivated to avoid pregnancy. In contrast, women who are assigned to start DMPA after a delay risk losing motivation to initiate use. To test this hypothesis, we will compare prevalence of use of a highly-effective contraceptive method at 12 months post-delivery between women in the intervention and placebo arms versus the open control arm. Secondary outcomes will include DMPA use at 12 months. Sensitivity analyses will evaluate 1) whether the findings differ by race and 2) whether the findings differ after restricting the intervention and placebo arms to the subset of women who believe that they were in the intervention arm.

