**No study on DMPA use during breastfeeding has assessed infant adiposity, specifically, as part of a more comprehensive assessment of growth.** Increased infant weight gain typically has been interpreted in the breastfeeding and DMPA literature as a positive outcome. However, early hormone exposure theoretically could promote adiposity at the expense of other growth, such as brain and lean mass. Also, excessively rapid infant weight gain, in general, is associated with lifetime cardiovascular risk and is an early indicator of obesity risk. Five cohort studies measured the effect of postpartum DMPA exposure on infant weight gain. The first study (N=331) comparing initiation of DMPA or norethisterone enanthate at either 7 or 42 days postpartum to a non-hormonal comparison arm found no difference between groups in infant weight gain in first three months. However, during months 4-6, infants in the two injectable arms had higher weight gain than those in the comparison arm. The four other non-randomized trials that evaluated infant growth found no difference in weight gain among breastfeeding infants of mothers using DMPA compared to infants in a comparison arm not using DMPA over six months, a mean of 18 months or 4.5 years, or a maximum of 17 years of postpartum follow up. Again, in these non-randomized studies the failure to control for important confounders related to women self-selecting use of DMPA precludes any firm conclusions. Furthermore, despite the assumption in these studies that increased weight gain is a positive outcome, the validity of this interpretation is unknown. By measuring adiposity, we will have a superior measure of the effect of the exposure.

**In summary, an inhibitory effect on breastfeeding from immediate postpartum administration of DMPA cannot be ruled out due to the lack of data from RCTs conducted in women, the failure to use validated measures of lactation and the reliance on crude measures of infant growth and adiposity. The data have important limitations:** short follow-up intervals, low power, lack of consistency in using sensitive and standardized outcome measures, and the lack of RCTs evaluating DMPA administration specifically in the immediate postpartum period.

**B. Literature in Support of Objective 2: The relationship between immediate postpartum initiation of DMPA and contraception use.**

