For secondary outcomes (breastfeeding duration, perceived adequacy of milk production, etc.), we do not have *a priori* set noninferiority margins, and thus a traditional superiority analysis will be conducted (test for significant differences using t-tests or chi-squared tests as appropriate). We will report two-sided 95% CIs for all outcomes so that post-hoc noninferiority analyses could be conducted (i.e., to evaluate whether the CI covers a specified noninferiority margin).

**Analysis of Objective 2.** A traditional superiority analysis will be used to compare rates of use of a highly effective method of contraception (defined here as DMPA, implant, IUD, sterilization, pill, patch, or ring) at 12 months post-delivery among women in the intervention or placebo arm versus those in the open control arm. An intent-to-treat analysis will be conducted using a chi-squared test to compare the percentages of women using contraception in each group (intervention + placebo versus open control). As a sensitivity analysis, we will repeat this analysis using logistic regression in order to account for potential confounders such as maternal age, parity, gravidity, socioeconomic status, sexual activity, and prior contraceptive history. We will also repeat analyses restricting those in the intervention or placebo arm to the subset of

women who believe that they received DMPA at enrollment regardless of the accuracy of their belief as an additional sensitivity analysis. Furthermore, we will evaluate whether the relationship between immediate postpartum DMPA initiation and contraception use at 12 months differs by maternal Black race.

Given that the contraception use outcome is measured at 12 months, we anticipate some missing data; however, we have no reason to believe dropout will be differential across arms. Thus, we will assess sensitivity of results to missing data using multiple imputation analyses under both missing at random and missing not at random assumptions. The secondary outcome (DMPA use at 12 months) will be analyzed with similar methods.

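### The two 4-month body-composition outcomes, %FM and FFM%, are complements, so the plan has one test in two forms and no direct estimate of lean mass; fat-free mass in kg would supply it at no cost

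*Combined protocol and SAP*

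**What the plan says.** Section V.C (Outcome Measures; the sentence is printed next to Table 2) lists five infant measures for the 4-month visit at OSUWMC. Item 1 is "percent fat mass (%FM) and fat-free mass (FFM%) measured using the validated" whole-body air displacement plethysmography system. The others are length, head circumference, "body weight with SECA 727 digital scale", and skinfold. Both abbreviations in item 1 carry a percent sign. No section lists fat mass or fat-free mass in kg, an index to length, or an analysis of body composition adjusted for weight or length.

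Section IV.A gives the reason for the measurement: "early hormone exposure theoretically could promote adiposity at the expense of other growth, such as brain and lean mass". It adds: "By measuring adiposity, we will have a superior measure of the effect of the exposure".

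Section V.E sets no noninferiority margin for secondary outcomes and plans a superiority analysis: "test for significant differences using t-tests or chi-squared tests as appropriate". It also says: "We will report two-sided 95% CIs for all outcomes so that post-hoc noninferiority analyses could be conducted".

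**The concern.** Plethysmography divides body mass into a fat and a fat-free part. Once %FM is known, FFM% is known, so the pair is a single outcome shown in two forms. A results table with both could be misread as two findings that agree.

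The larger point is the match between outcome and rationale. Section IV.A worries about fat gained at the expense of lean tissue. A percentage is a ratio. It rises if fat rises or if lean tissue falls, and it stays put if both change in proportion. A difference in %FM, taken alone, does not say which part of the body changed, and no difference in %FM, taken alone, does not show that lean mass is equal. If lean growth is to be discussed in the report, the plan should contain an outcome that measures it.

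**Working it through.** The documents give no expected value, standard deviation, effect size or power for body composition, so there is no stated figure to reproduce. All body-size values below are assumptions for illustration: weight 6.5 kg (SD 0.6 to 0.8 kg) and %FM 25 (SD 4.5).

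**1. The two percentages are one test.** FM + FFM = weight, so FFM% = 100 − %FM. The mean difference changes sign, the standard deviation is unchanged, and so t changes sign while p stays the same. In 2,000 simulated two-sample comparisons (143 vs 286), the largest |t₁ + t₂| was about 9 × 10⁻¹⁴ and the largest difference in p about 5 × 10⁻¹⁴, which is rounding error.

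**2. Same percentages, different lean mass.** FFM = weight × (1 − %FM/100).
- 6.5 × 0.75 = 4.875 kg
- 6.2 × 0.75 = 4.650 kg
- Difference: 0.225 kg of fat-free mass, with zero difference in %FM and FFM%.

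**3. Same change in the percentages, different causes.** Start at 6.5 kg and 25% fat (FM 1.625 kg, FFM 4.875 kg) and go to 27% fat.

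| Cause | FM (kg) | FFM (kg) | Change in FFM (kg) | Weight (kg) |
|---|---|---|---|---|
| Fat gain, lean unchanged | 4.875 × 0.27/0.73 = 1.803 | 4.875 | 0 | 6.68 |
| Swap at constant weight | 6.5 × 0.27 = 1.755 | 6.5 × 0.73 = 4.745 | −0.130 | 6.50 |
| Lean loss, fat unchanged | 1.625 | 1.625 × 0.73/0.27 = 4.394 | −0.481 | 6.02 |

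The percentages are identical in all three rows. Weight is not: it rises by 0.18 kg, stays level, or falls by 0.48 kg.

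**4. What weight already detects.** Take a uniformly 5% smaller body: weight lower by 6.5 × 0.05 = 0.325 kg, FFM lower by 4.875 × 0.05 = 0.244 kg, %FM unchanged. For weight, SE = SD × √(1/n₁ + 1/n₂). At 70 vs 140 this is 0.088 kg (SD 0.6) or 0.117 kg (SD 0.8), so 0.325/SE is 3.70 or 2.78. The table shows rejection rates at two-sided 0.05, calculated for weight and simulated for the other two.

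| Infants (intervention vs other two arms) | %FM or FFM% | Weight | FFM in kg |
|---|---|---|---|
| 70 vs 140 | 5–6% | 79–96% | 72–88% |
| 114 vs 228 | 4–5% | 94–99.7% | 88–97% |
| 143 vs 286 | 5–6% | 98% to above 99.9% | 96–99.5% |

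The group sizes are also illustrative: 143 vs 286 is full randomization, 114 vs 228 applies the 20% attrition that the plan assumes at 12 months, and 70 vs 140 allows for further loss because only one site does the visit.

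**5. What remains missing.** Weight shows that the infants are smaller, but not how the difference divides into fat and lean. That split cannot be recovered exactly from separate summaries of weight and %FM. With p = %FM/100, the mean of W(1 − p) equals mean(W) × (1 − mean(p)) − Cov(W, p), and its standard error also depends on how W and p vary together. It needs FFM calculated for each infant.

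**The case against.** The strongest case against is that the plan does not rest on the percentages alone. Body weight is a secondary outcome at the same visit, with its own test and interval. It separates the two extreme routes from 25% to 27% fat by 6.68 − 6.02 = 0.66 kg, and it detects a uniformly smaller body at least as well as FFM in kg would. Head circumference speaks to brain growth. A swap of fat for lean at constant weight, the trade-off that Section IV.A describes, does move %FM. Every input for FM and FFM in kg is collected, so both can be derived at any time. All of this stands, and it rules out several stronger readings.

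- A reader might infer that the planned outcomes cannot tell fat gain from lean loss. The documents do not support this: %FM read with weight goes a good part of the way.
- A reader might infer that a proportional loss of fat and lean is what reduced milk supply would produce, so that a null %FM result would hide the likely harm. No section says so. The 5% case above is an illustration only, and weight would show it.
- A reader might infer that the duplicate inflates type I error. It does not, because the two tests always agree.

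The wording also leaves a small chance that an absolute mass was meant by FFM. The percent sign suggests otherwise, and if kg was intended the label needs correcting.

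What the objection does not supply is a lean-mass estimate with an interval among the listed outcomes. One derived after the data are seen would be post hoc.

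**Conclusion.** The point holds in a limited form. %FM and FFM% carry the same information, and neither alone estimates the lean mass named in the rationale. Weight, length and head circumference partly fill the gap when read with %FM, but no listed outcome gives a direct estimate and 95% confidence interval for lean mass. The identity is exact for any fat/fat-free split. The sizes (225 g at equal percentages; 0 to −481 g of lean mass behind the same two-point rise in %FM) rest on the assumed weight and fat percentage. This is a minor, no-cost improvement to a secondary outcome measured at one site. It does not affect the primary outcome, the sample size or the conduct of the trial.

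**What to change.** In Section V.C, replace FFM% with absolute fat-free mass (kg), and list absolute fat mass (kg) beside %FM. Take both from the plethysmograph output, or calculate them per infant as FM = weight × %FM/100 and FFM = weight − FM. In Section V.E, state that any conclusion about lean growth will rest on the difference in FFM in kg and its 95% confidence interval. Indexing FM and FFM to length squared is optional, since length is measured at the same visit.

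The cost is a change of wording, with no new visit, procedure or data item. It should be made before the 4-month data are compared by arm, so that the outcome counts as pre-specified.

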#### **D. Detailed Study Procedures**

**Recruitment.** We will advertise the study to women in the community during their pregnancy and to postpartum women following delivery at the study site before their discharge (Table 2). This recruitment will use a motion graphic video, which can be accessed through women's own electronic devices (see <http://go.osu.edu/ppfpstudy>). Postpartum patients also can choose to watch the video through the MyChart Bedside tablets at OSUWMC or tablets at Emory-affiliated hospitals via a home screen icon for the video. The URL and QR code for the video are included on the study written materials (poster and brochure). The video describes the following to potential participants: 1) the risk of pregnancy following childbirth among women who are sexually active, but not using a modern contraceptive method, even if the woman is breastfeeding and menses has not yet resumed; 2) benefits of using DMPA to adequately space pregnancies for both maternal and infant health; and 3) overview of the trial.

The approved MyChart message (see file "MyChart Message") will be routed monthly to the subset of OSUWMC and Emory patients who are identified in a query through the Information Warehouse that fit the study inclusion criteria by an Honest Broker. Specifically, the message will be sent only to patients of OSUWMC and participating Emory-affiliated hospitals who are 1) a living patient; 2) active MyChart user; 3) attended a patient visit within the past year; 4) currently pregnant; 5) expect to deliver at a participating hospital; and 6) have an estimated delivery date within the next month.

These patients will receive an email notifying them that they have "A new research study to view" in their MyChart message file. Once they login to their secure MyChart they will be able to review the details of the message and express their interest or decline more information. A "yes" response will release their contact information to the researcher in IHIS. If the volunteer clicks "no" or ignores the message, the researcher will not receive any information about the potential volunteer. The list of MRNs (obtained through IW) will go directly to Research IHIS team. The Research IHIS team will use the identified MRNs to send messages via MyChart. Only the Patients who said "Contact Me" (accepted) the medical record will be viewable by study team.

**Screening, enrollment and randomization.** Study staff will use the "Eligibility Assessment Form" to screen pregnant and postpartum women who are recruited for the study to determine whether they meet the eligibility criteria.

If they have not already watched the recruitment video, eligible women will be given a tablet and headphones and asked to watch the video. They then will be asked to read the “Combined Consent Form” in a private location. Women will indicate their agreement to participate in the study by signing the “Combined Consent Form.” Women will be given an unsigned copy of the “Combined Consent Form” to keep for future reference, as it provides contact information for staff responsible for the conduct of the research study in the event of any questions or concerns.

If screening and signing of the “Combined Consent Form” occurs during the prenatal period, the participant will be rescreened – using the same “Eligibility Assessment Form” – after delivery before randomization. In this case, rescreening is to ensure that she meets the eligibility criteria before randomization.

Randomization will occur after delivery (ideally within 48 hours) and before hospital discharge. Stratified randomization with random permuted blocks will be generated using the randomization function within the electronic data capture system, REDCap. This process serves to conceal the allocation process by automatically revealing the arm assignment only upon study enrollment. To minimize the potential for attrition or crossover between arms, participants who are randomized to the intervention or placebo arm will be administered their assigned shot (under blinded conditions) immediately after randomization. Research pharmacy staff will ensure the correct shot is given to the correct participant by checking the randomization documentation before dispensing.

Participants will complete the “Enrollment Questionnaire” on demographics, reproductive history, attitudes and intentions on related topics including breastfeeding.

Participants will be referred for DMPA at 12 weeks if in the intervention or placebo arms and at 6 weeks if in the open control arm. Participants will receive referrals for financial assistance for DMPA as appropriate. Participants will be counseled to use condoms for all sexual intercourse before receiving DMPA and will receive a supply of condoms for 12 weeks (intervention or placebo arms) or 6 weeks (open control arm). Interviewers will administer the short “Milk Let-Down Questionnaire” up to three times daily in person before discharge or until lactogenesis II occurs.

**Follow up.** If lactogenesis II does not occur before hospital discharge, participants will be asked to complete the “Milk Let-Down Questionnaire” daily via telephone, text or email for the first 7 days postpartum until the event occurs.

Participants will be instructed to complete an online “Follow-up Questionnaire” at 1, 2, 4, 6, 9 and 12 months post-delivery. The “Follow-up Questionnaire” will collect data on breastfeeding behaviors and perceptions; contraception use; and infant physical measurements from well-child visits. If the participant does not have the information from her infant’s well-child visit on-hand or if the information that she provides is incomplete or appears to be inaccurate, we will extract the data on the infant’s weight, length and head circumference from the medical records at their pediatrician’s office.

Participants enrolled at OSUWMC will be asked to return with their infant to OSUWMC for a four-month visit, during which infant measures will be collected (infant adiposity via PEA POD, weight, length, head circumference and skinfold) and recorded on the “Four-month Visit Form.” If women have not already completed their 4-month online “Follow-up Questionnaire” at the time

of the in-person visit, they will be instructed to do so using a computer established for this purpose at OSUWMC.

**Compensation.** Participants will receive compensation (amounts specified in Table 1) for their time and travel expenses. The compensation amounts are in-line with recent research with similar populations.

**Blinding.** Blinding of the investigational product is critical to the integrity of the study. Participants and study staff will be blinded to the study drug assignment to the intervention and placebo arms. The Investigational Drug Services (IDS) Pharmacy at the study sites will have responsibility for organizing the blinding and preparing the injections. The IDS Pharmacy provides support to clinical trials at the study site and operates in compliance with all relevant regulatory and institutional policies. An unblinded pharmacist will prepare the injections in such a way as to ensure the masking of the contents of the syringe. The three study arms will receive the following: 1) intervention arm will receive DMPA injection; 2) placebo arm will receive 0.9% sodium chloride injection; and 3) open control arm will receive no injection. After completion of randomization and treatment allocation, study medication (i.e., DMPA injection or 0.9% sodium chloride injection) will be withdrawn into a 1mL syringe. Syringes will be masked using amber tinted tape to ensure blinding (see Figure 2).

**Data collection and management.** All study data will be recorded into the PHI version of the electronic data capture system, REDCap. Supported by the OSU Center for Clinical and Translational Science (CCTS), REDCap facilitates the transmittal of secure, encrypted and password-protected data. CCTS will program the data entry screens (with audio component options for participant-administered questionnaires), implementing built-in skip patterns and quality control checks. Data will be instantaneously uploaded behind the secure OSU firewall. The PI will monitor data during the study to resolve potential issues upon detection.

Participants' privacy and the confidentiality of data will be protected through training of interviewers and other study staff; conducting all interviewing, and physical examinations in private; storing study materials in a locked room; and securing computer files that include identifiers. The linkage between the PINs and the participants' identifying information will be maintained in a REDCap form. Otherwise, only the study PINs will identify participant research records. The form with the linkage between the PINs and the participants' identifying information and all other identifying information (e.g., signed consent forms) will be destroyed after the primary trial findings are published. Data identifying individual study participants will not be published or released to persons outside of the project. Non-identifiable study data will be retained for at least five years after study close-out.

**Minimizing attrition.** We will implement strategies used by the study team in other studies that have achieved high retention of participants during follow up. These targeted efforts will include 1) providing information to participants at each encounter about the importance of attending the scheduled study visits or completing the telephone or online questionnaires, 2) providing

